### 2.1. Organisational Relationships of CCP-CANCER UK

This CCP-CANCER UK study was conceived in the University of Liverpool, and developed with collaboration and intellectual input from investigators in University of Liverpool (UoL), University of Edinburgh (UoE), Imperial College London (ICL) and the University of Oxford (UoO), as well as representatives for patient and public involvement (PPI). The funding application was led from UoL and the study will be facilitated through the Liverpool Clinical Trials Centre (LCTC) within UoL. The study is based upon the CCP UK study which is sponsored by The University of Oxford and led from UoL (the CI is based at UoL). The University of Oxford hosts the REDCap database for the parent CCP UK study for which they are also the data controller.

Clatterbridge Cancer Centre NHS Foundation Trust (CCC) agreed to act as sponsor for CCP-CANCER UK because of their special interest in cancer research and how COVID-19 impacts their patients with cancer. In addition, several investigators hold substantive or honorary contracts with CCC. Data controllership for the study rests jointly with UoL, UoE and CCC. The organisations are considered CONTROLLERS under GDPR for the following reasons:

- 1. CCC as they will act as sponsor and will carry overall responsibility for the initiation, management and financing (or arranging the financing) of the research.
- 2. UoL as they conceived the project and decided the need to collect and process data alongside having overall responsible for the day to day running of the study and the data collection
- 3. UoE as they will have significant input into the identifying the research question, determining the dataset and developing and delivering the Statistical Analysis Plan. They will also determine on which patient's data will be collected from and make decisions on how data from the study will be processed and analysed in the National Safe Haven.

The 3 parties will enter in a tripartite joint data controller agreement with regard to the CCP-CANCER UK study.

The NHS Scotland National Safe Haven Hub located in Edinburgh will house the data but have no part in determining the analysis plan (data processor). For CCP-CANCER UK, Oxford will share NHS numbers with the tripartite (securely transmitted to UoE). This will be done via a CONTROLLER to CONTROLLER agreement.

Public Health Scotland (PHS) hosts, and has governance responsibility for the NHS Scotland National Safe Haven, a trusted research environment which is not connected to the internet in which personally identifiable data can be linked and processed. For the purposes of this protocol, an agreement will exist between the tripartite and PHS covering use of the National Safe Haven.

Once the data are analysed, manuscripts will be drafted and circulated among all the institutions and investigators that have been involved. This will follow the same principles as have applied to the parent ISARIC4C CCP UK study.

[figure not shown]
These relationships are summarised in the table and figures on the following page.

On behalf of the Data Controllers, named statistician(s) from LCTC will be granted access to the NHS Wales National Safe Haven, known as the Secure Anonymised Information Linkage (SAIL) Databank. Access is granted via an affiliation to the 'One-Wales' COVID project within SAIL, also known as 'Con-Cov' (SAIL reference 0911 – WMC\_), therefore an agreement with NHS Wales is not required. Analysis of data for Welsh patients is described in the relevant statistical analysis plan.

	Agreement	Parties	Brief summary of content
1.	Service Level Agreement	CCC and UoL	Delegates' responsibilities for day to day running of the study from CCC (Sponsor) to UoL (LCTC).
2.	Collaboration agreement	UoE, UoL and CCC	Defines academic ownership, publication policy, and finance for employment of data analyst in Edinburgh. Incorporates agreement of joint Data Controllership.
3.	Data Sharing Agreement	CCC, UoL and UoE, UoO	Defines the relationship between the three organisations ("The Tripartite"), roles & responsibilities with respect to data and data controllership. Includes the relationship between The Tripartite and University of Oxford (UoO) with respect to UoO providing data from the CCP-UK study. This will form a schedule to the contract described in point 3 below.
4.	Data processing agreement	UoE, CCC, UoL and PHS	Covers the hosting of data within the Scottish National Safe Haven. UoE to take on responsibility for liability for this relationship, as outlined in the Tripartite JDC.

#### Brief summary of agreements relating to the CCP cancer UK study

Figure 1: Organisational relationships of agreements

# 3. Introduction

### 3.1. Background

In December 2019 the first pneumonia cases of unknown origin were identified in Wuhan, the capital city of Hubei province. High-throughput sequencing revealed the pathogen to be a novel enveloped RNA beta coronavirus. Initially named 2019 novel coronavirus (2019-nCoV) it was subsequently renamed severe acute respiratory syndrome coronavirus 2 (SARS-CoV-2) (2). Transmission of SARS-CoV-2 is via respiratory droplets and direct contact, and infection results in coronavirus disease (COVID-19). The World Health Organization (WHO) has recently declared the SARS-CoV-2 outbreak a public health emergency of international concern on 30th January 2020, and a global pandemic on 11th March 2020.

The clinical characteristics of COVID-19 are typically fever, dry cough and fatigue, sometimes accompanied by sore throat, chest discomfort and difficulty breathing. However, a wide range of other symptoms are possible, including gastrointestinal symptoms such as nausea, vomiting, loss of appetite, abdominal pain and diarrhoea. Loss of taste and smell have also been described.

Individuals with malignant disease are more prone to respiratory viruses than individuals without cancer as a result of immunosuppression caused by either the underlying disease process or systemic anti-cancer therapy. The death rate from influenza in patients with solid organ tumours is much higher than expected for the background population, even allowing for likely ascertainment bias. This is reflected in individuals with cancer being recommended to receive the seasonal flu vaccination. Certain groups of cancer patients are even more prone to infection. For example, patients with haematological malignancy undergoing bone marrow transplantation have significant mortality even with rhinovirus, which can double the transplant related mortality.

There is currently no prospective robust data regarding the presentation, management and outcome of patients with COVID-19 with cancer who are immunocompromised as result of either the disease or treatment. Furthermore, it is not clear if the immunosuppressive effects of systemic anti-cancer therapy such as chemotherapy are the same across all cancer types and the possible risks entailed by targeted therapies and immunotherapy. Currently, cancer patients on treatment are considered at high risk group of possible severe infection with SARS-CoV-2 and measures such as self-isolation are being recommended to mitigate the risks of such patients being infected. However, information to inform this decision, and whether any specific sub-groups of patients are at particular risk is lacking. These data are vital to inform policy on cancer treatments as patients may be potentially exposed to SARS-CoV-2 for a long time to come. Furthermore, given patients with cancer are often immunosuppressed and this may alter the clinical presentation as well as clinical course and outcomes. Different tumour types may also have implications for SARS-CoV-2 exposure, for example patients with lung cancer may be more susceptible, and require different pathways to ensure care can be delivered safely. This protocol aims to describe the presentation, management and outcomes of patients with solid and haematological malignancies with COVID-19 and compared to non-cancer patients. The CCP-CANCER UK will provide valuable information that would educate as well as help inform current practice and development of guidelines globally with regard to COVID19 infection in cancer patients. While samples collected within CCP-UK from cancer patients will enable an understanding of the biology of COVID-19 in the setting of cancer-related immunodeficiency both innate and iatrogenic.

### 3.2. Rationale

Currently, there is extremely limited information regarding the risks posed by SARS-CoV-2 to patients with cancer. This study aims to understand the presentation, management and outcomes of patients with cancer. The influence of cancer type and treatment will be explored as well, and the existence of a large dataset of COVID patients including both cancer patients and patients without cancer, allows a comparison between these two groups which can be

adjusted for other confounding variables such as age and co-morbidity. This dataset, on robust analysis, will provide valuable information that would educate as well as help inform practice for future possible outbreaks. The information may also inform the development of guidelines with regard to the care and management of cancer patients with viruses such as COVID19 and similar infectious diseases. Cancer is immunosuppressive, the nature of the immunosuppression seems to be influenced by the microbiota, and in addition pulmonary infections are also influenced by the host microbiota, therefore it is important to understand this impact in cancer patients.

The complexity and rapidly evolving nature of cancer therapies and in particular, molecularly targeted agents also may predispose patients to COVID-19. We propose to, where available in future, also take sequencing/genomic data through data linkages for patients recruited into CCP-CANCER UK will be used to outcomes to explore genetic susceptibility to COVID-19, the effects of molecularly targeted agents as well as predictors of severity and death from COVID-19.

Serial faecal samples and throat swabs are being collected from patients as part of the CCP-UK, and the ISARIC -Coronavirus Clinical Characterisation Consortium (ISARIC4C) is already carrying out extensive metagenomics sequencing including 16/18S sequencing and Illumina RNAseq. These data provides crucial detail on co-infection and also would allow an overview of microbiome diversity in patients with COVID-19 and how it changes during disease progression and treatment. This could be used as background to a more targeted and deeper analysis of the cancer patients in the cohort. Outcomes for patients with respiratory tract infections [1, 2] and various forms of cancer [3-6] have been shown to be influenced by respiratory and gastrointestinal microbiome diversity. Analysis of the microbiome can also help in directing therapy [7, 8], in particular the use of immunotherapy [9].

### 3.3. Objectives

The overall objective of the CCP-CANCER UK is to provide information that would educate as well as help inform current practice and development of guidelines globally with regard to COVID-19 infection in cancer patients, in both haematological and solid malignancies (ICD-10 CO0x to D49x, all morphologies). We will use data linkages to supplement the CCP-CANCER UK dataset and details of data linkages can be found in the sections below.

#### Co-primary Objectives\*

The co-primary objectives are:

- To determine the COVID-19 fatality rate overall in the cancer population using the most up to date dataset from the first wave
- To identify factors associated with poor outcomes from COVID-19 in patients with cancer.

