# 1 Study Overview

# **1.1.1** Study Overview - CCP-CANCER UK (Companion study)

[figure not shown]
Full Title:	Clinical Characterisation Protocol for Severe Emerging Infections in the UK (CCP-UK) – A prospective companion study for patients with cancer and COVID-19.	
Acronym:	CCP-CANCER UK	
Phase:	Prospective observational cohort study, with routine healthcare data linkage.	
Target Population:	Patients with COVID-19 who have with a diagnosis of a solid or haematological malignancy (D or C codes of ICD-10). The main population will be from patients who have been recruited to the UK Clinical Characterisation Protocol (CCP-UK) study.	
Sample size:	5000 completed datasets	
Inclusion Criteria:	Patients with proven COVID-19 and a diagnosis of cancer, as defined by either a past medical history recorded using the CCP-UK case report form, or who have a recorded diagnosis (C00-D49 ICD-10, or relevant equivalent i.e. ICD-9) in national cancer registries, who are enrolled into any Tier of the Principal CCP-UK protocol.	
Exclusion Criteria:	None in addition to those specified in the Principal CCP-UK protocol.	
Study Centres and Distribution:	Any healthcare facility in the UK who are participating in the CCP-UK study. To ascertain the number of cancer patients in the UK who have had SARS-CoV-2 infection, we will also request linked routine healthcare data for the UK, for all individuals with a cancer diagnosis, not just those in CCP-UK.	
Nature and duration of patient participation:The CCP-CANCER UK companion study involves the coll additional data from patient case records. It does not re additional patient visits, assessments or sample collections as all integral to the Principal CCP-UK protocol.		
Study Duration	There will be three components of the study that run concurrently: Additional data collection for patients in CCP-UK with cancer The study will remain open for at least 2 years post first patient registration onto CCP-CANCER UK. All retrospective patient data collection will begin as soon as each site receives the greenlight to do so,	

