and all prospectively enrolled patients (on to CCP UK) who meet inclusion criteria will have their data collected.Co-enrolment of patients with COVID and cancer diagnosisPatients who meet the eligibility criteria for the CCP-UK study and CCP- CANCER-UK can be co-enrolled prospectively into both studies.Data linkageLinkage to routine healthcare data (cancer registries, primary healthcare data, secondary healthcare data and testing data) will occur on one occasion only.Data will be retained for 15 years at the end of study.Co-primary objectives:To determine the mortality rate in patients with cancer and COVID-19, using data from the CCP-UK study and linked data. Identify factors associated with the poor outcomes in patients with cancer and COVID-19.Secondary objectives:The CCP-UK and CCP-CANCER-UK case report forms will be combined with linked data to: Describe the clinical features and severity of COVID-19 in different tumour types.Determine the influence of disease stage, treatment intent and treatment history on severity and COVID-19 fatality rate. Determine the influence of disease stage, treatment intent and treatment history on severity and COVID-19 fatality rate. Determine the outcome of COVID-19 in different tumour types. Determine the outcome of COVID-19 in different tumour types. Undertake a matched cohort study using the cancer and non-cancer patients with COVID-19 in different tumour types.Exploratory/Translational objectives:To investigate the biology of SARS-CoV-2 in the context of cancer- associated or latrogenic immunosuppression. To investigate how COVID-19 interacts with cancer related immunosuppression.			

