#### 5. Eligibility Criteria

The CCP-CANCER UK study aims to recruit all patients infected with SARS-CoV-2 and enrolled onto the Principal CCP-UK protocol and identified as having a neoplasm (Malignant, in situ, or benign haematological cancer or solid tumour). Recruitment will continue for up to 2 years.

The eligibility criteria are described below.

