## 6.4.4 Data linkage to determine population level risks in UK cancer patients

In addition to taking data from the ISARIC CCP-UK study, which provides a focussed look at in-hospital treatment of patients with COVID-19, to be able to generalise our findings to a national population, we will need to establish how many cancer patients develop COVID-19 and their subsequent treatments and outcomes. To do this, we will use linked data that are not restricted to the ISARIC CCP-UK study and instead take all individuals with cancer registration data available and link these to SARS-CoV-2 testing data, primary care data, secondary care data and national statistics registrations.

Data will be requested according to the same specification provided to cancer registry linkage providers and will request additional data points held in testing data, primary care data, secondary care data and national statistics registrations. Data flow will be from the providers directly into the Scottish National Safe Haven, as no patient identifier lists will be required.

These data will allow us to determine which populations are at the highest risk of COVID-19, both in hospital and in the community and establish a baseline rate in these settings. This will allow us to establish whether there are

particular patient groups who are more likely to be admitted to hospital or who will go on to die while in hospital, compared to patients who do not die or who remain in the community with positive tests. We request data for all patients, both for those with negative and positive SARS-CoV-2 tests or diagnoses. These data will also enable us to determine whether changes in practice have led to improved or worsened cancer outcomes over the time of the SARS-CoV-2 pandemic.

The data will not contain any identifiers and will not be able to be linked with the ISARIC CCP-UK or CCP-CANCER UK datasets.

For data linkage, we will capture variables including lower super output area. This will be used to map individual region rates of SARS-CoV-2 and determine other geographical variables including deprivation, distance to healthcare facilities and other socioeconomic deprivation markers linked with geography. We will not capture information on hospital of treatment in the linkage requests, as this will provide too logistically challenging to match back to hospital for recruitment purposes.

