### 6.4.5 Data minimisation

We will actively collect data from the eCRF, both retrospectively on patients who have been recruited to the CCP-UK study and prospectively for patients who will be co-enrolled into both ISARIC CCP-UK and CCP-CANCER-UK. The eCRF will obtain clinically specific treatment and stage data that are not available from sources of routine healthcare linkage. Details on existing comorbidities, tumour stage, treatments and clinical outcomes will be collected using linkages to sources of routine healthcare data. Data from these linkages will also give us data not available from the eCRF and allow efficient follow-up. There may be potential overlap between the two data sources. This is justified on the basis of ensuring the most complete coverage possible, in the fastest possible time, as linked data has a delay associated with it. Whilst it would be possible to collect these data in series instead of in parallel, this would take considerably longer, and would give rise to an unacceptable delay in providing our outputs for the benefit of patients, the public, policy makers and clinicians.

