#### Matched Cohort Study

Using the whole CCP-UK prospective observational cohort, we will perform a matched cohort study. We will match cancer patients and non-cancer patients within the main dataset by age, sex, race and comorbidities. We will determine which factors are associated with fatal outcomes for patients with cancer, particularly with respect to cancer type, stage, immune suppressive or immune modulating/immunotherapy treatment, treatment intent and time from diagnosis.

Data from the CCP-CANCER UK CRF will be supplemented by linked data. Where a data field is discussed that does not appear in the linked data specification, it will be present in the electronic CRF.

We will examine the effects of the following variables on mortality and severity of COVID-19 in cancer patients:

- Age, Sex, Co- morbidities
- Tumour type
- Solid versus haematological malignancy
- Bone marrow transplant
- Stage of malignancy at time of COVID-19 (from CCP-UK CRF) and stage at diagnosis from data linkage.
- \*Diagnosis of malignancy in the last: 1-4 weeks, 1-6 months, 6 months -1 year, 1-5 years, > 5 years
- \*Surgery or Chemotherapy or radiotherapy treatment in the last: 1-4 weeks, 1-6 months, 6 months -1 year,
- > 1 year
- ¥Other systemic anticancer therapy in the last: 1-4 weeks, 1-6 months, 6 months -1 year, > 1 year
- Intent of treatment: Curative vs (neo)adjuvant vs palliative vs watch and wait
- Use of corticosteroids
- Use of Granulocyte colony-stimulating factor

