### 8.4. Analytical Methods

#### 8.4.1. Patient Groups for Analysis

Primary analysis will be performed on an 'Intention to Treat' (ITT) principles which will analyse all patients identified with cancer and a COVID-19 diagnosis unless there are sound reasons to remove them from the analysis. Various exploratory sub-group analyses may also be performed and these will be fully justified either in the statistical analysis plan or the final statistical report.

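### The first co-primary fatality rate has two populations, an undated first wave or all patients, and the matched cohort omits the COVID-19 date from its matching variables

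*Protocol*

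**What the plan says.** On the population, section 3.3 gives the first co-primary objective as "To determine the COVID-19 fatality rate overall in the cancer population using the most up to date dataset from the first wave". No start or end date for the first wave appears. The overview in section 1.1.1 words the same objective as "To determine the mortality rate in patients with cancer and COVID-19, using data from the CCP-UK study and linked data", with no wave limit. Section 8.4.1 says that the primary analysis will "analyse all patients identified with cancer and a COVID-19 diagnosis unless there are sound reasons to remove them from the analysis".

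On enrolment, section 6.4.5 collects data retrospectively and also "prospectively for patients who will be co-enrolled into both ISARIC CCP-UK and CCP-CANCER-UK". Section 1.1.1 says "The study will remain open for at least 2 years post first patient registration onto CCP-CANCER UK", while section 5 says "Recruitment will continue for up to 2 years".

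On the cancer comparison, section 8.2 (Matched Cohort Study) states: "We will match cancer patients and non-cancer patients within the main dataset by age, sex, race and comorbidities". The list of variables to be examined that follows contains no calendar variable. A footnote to section 3.3 extends the comparison with non-cancer patients to all objectives. Section 8.4.4 describes logistic models that adjust for possible confounders without listing them, and section 8.1 leaves full detail to separate statistical analysis plans.

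**The concern.** A fatality rate needs one denominator. Here the objective points to a subset defined by a period, while the overview and the analysis set point to everyone. A SAP cannot carry out both, and the choice changes which patients the headline result describes.

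The matching issue follows from the second reading. If the data span several periods, a cancer patient can be matched to a control of the same age, sex, race and comorbidities who was infected at a quite different time. Any difference in fatality between the periods then enters the cancer comparison wherever the two groups are spread differently over time.

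The two parts are partly alternatives. A first-wave set would remove differences between waves, although drift within the wave could remain. An all-period set is exposed to them.

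**Working it through.** **Population, side by side**

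| Place | Population for the fatality rate |
|---|---|
| 3.3, co-primary objective | First wave, undated |
| 1.1.1, same objective | Patients with cancer and COVID-19; no wave limit |
| 8.4.1, primary analysis set | All patients with cancer and COVID-19 |
| 8.4.4, primary endpoint | Deaths over patients with a positive diagnosis; no wave limit |
| 8.2, sample size | 5000 patients; not tied to a wave |

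Section 6.5 also sends completed data for an updated analysis every 3 months, which does not describe a closed first-wave cut. The decisive conflict is 3.3 against 1.1.1 and 8.4.1; the enrolment period only supports it. The two duration statements give a floor and a ceiling. If they describe the same window, they agree only at exactly two years. If they describe different windows, the protocol does not say so.

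**Precision under the two readings**

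The plan's own figure is a 95% interval about 3% long (8.5% to 11.5%) for 10% fatality in 5000 patients. It does not reproduce: length = 2 × 1.96 × √(0.10 × 0.90 / 5000) = 1.66%, or 9.2% to 10.8%. That is a separate error, and the present point does not rest on it. The same formula shows what a first-wave limit would cost. The first-wave share is not given, so these shares are assumed:

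| First-wave share of 5000 | n | Interval length at 10% fatality |
|---|---|---|
| 100% | 5000 | 1.66% |
| 75% | 3750 | 1.92% |
| 50% | 2500 | 2.35% |
| 25% | 1250 | 3.33% |

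**Calendar period in the cancer comparison**

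The protocol gives neither fatality by period nor the timing of cancer and non-cancer cases, so every input here is assumed. Take two periods with fatality f1 and f2, identical in cancer and non-cancer patients (true odds ratio 1). Let a be the share of cancer patients in the early period and b the share of controls. Assume that matching on age, sex, race and comorbidities does not happen to balance period.

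Cancer fatality = a·f1 + (1 − a)·f2. Control fatality = b·f1 + (1 − b)·f2. The crude odds ratio is the ratio of the two odds. For f1 = 15%, f2 = 5%, a = 50%, b = 40%: cancer 10%, control 9%, odds ratio (0.10/0.90)/(0.09/0.91) = 1.12.

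| Fatality early, late | Early share: cancer, control | Fatality: cancer, control | Crude OR |
|---|---|---|---|
| any | equal | equal | 1.00 |
| 15%, 10% | 50%, 40% | 12.5%, 12.0% | 1.05 |
| 15%, 5% | 50%, 40% | 10%, 9% | 1.12 |
| 15%, 5% | 40%, 50% | 9%, 10% | 0.89 |
| 15%, 5% | 60%, 30% | 11%, 8% | 1.42 |
| 15%, 5% | 30%, 60% | 8%, 11% | 0.70 |

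The direction follows the sign of a − b. The size needs both a fatality difference and an unequal mix.

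**The case against.** The strongest reply is that a two-year enrolment can coexist with a first-wave data cut for one objective. That is right, and duration alone would prove nothing. It does not explain why the same objective appears elsewhere without the limit, or why the primary analysis set has none.

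A reader might infer that the regression models also ignore calendar time. The documents do not support this. Section 8.4.4 leaves the adjustment set open, and the SAP that would fill it is not shown. The list in section 8.2 names variables whose effects will be examined; it is not a closed list of confounders. Only the matching variables are fixed in the protocol.

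A reader might also infer that the protocol itself expects fatality to change over time. Section 6.4.4 asks only whether "changes in practice have led to improved or worsened cancer outcomes over the time of the SARS-CoV-2 pandemic". That is an open question about cancer outcomes, put to a separate population dataset that cannot be linked to this cohort.

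Nor is it shown that cancer patients were admitted at different times from controls. Section 3.1 says that self-isolation was recommended for cancer patients on treatment. That makes different timing possible, but it gives no figures and does not say in which period cancer cases would concentrate.

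Finally, the matched cohort is a secondary objective. That stands, although the footnote to section 3.3 carries the non-cancer comparison to every objective.

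**Conclusion.** The contradiction in the co-primary population is plain on the face of the protocol and needs no assumption. As written, the plan supports two different primary results, and one of them has no dated boundary.

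The missing matching date is a real but conditional weakness: calendar period may bias the cancer comparison, and it has not been shown to do so. In the assumed scenarios a true odds ratio of 1 appears as 0.89 to 1.12 under a modest imbalance (50% against 40%, with fatality of 15% then 5%). Under a marked one (60% against 30%) it appears as 0.70 to 1.42. It stays at 1.00 if the period mix is equal.

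It would be tempting to set these values against a significance limit derived from section 8.2. That section's precision statement concerns a 70:30 factor among 5000 cancer patients, and the protocol gives no matching ratio or precision for the matched comparison. Whether a bias of this size would reach significance therefore cannot be said.

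**What to change.** 1. Define the population of the first co-primary objective once, by calendar dates, and use identical wording in sections 1.1.1, 3.3 and 8.4.1. One workable form is all periods, with fatality also shown by period and the first wave as a dated stratum.
2. Reconcile the duration statements in sections 1.1.1 and 5, saying whether each refers to recruitment or to the study being open.
3. Add COVID-19 admission or diagnosis date, or calendar period, to the matching variables in section 8.2, or adjust for it in the matched analysis. Name it among the confounders for the logistic models in section 8.4.4.

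The cost is protocol and SAP wording. The date is already needed, because time to death (8.3.2) runs from COVID diagnosis and the treatment and diagnosis windows (8.2) are counted from the COVID-19 episode. Matching on one more variable leaves somewhat fewer eligible controls for some cancer patients; how many cannot be judged, since the size of the control pool is not stated. Adjusting for the date instead avoids that loss.
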